5.4.1 Inclusion Criteria

- Subject is able to provide informed consent to participate in the study;
- Subject diagnosed with chronic intractable pain associated with back and/or limbs;
- Subject is 18 years of age or older;
- Subject has failed to respond to at least 6 months of conventional treatment which may include pharmacological treatment, physical therapy, epidural injections;
- Subject has a back and/or leg pain intensity of at least 6.0 cm out of 10.0 cm on the average back and/or leg pain VAS at baseline;
- Subject's medical record has been evaluated by the Investigator to ensure that the subject is a
 good candidate for a neurostimulation system;
- Subject is on stable pain medications with a total opioid for at least 28 days prior to enrolling in this study, and is willing to stay on those medications with no dose increase until the 3 month visit;
- Subject is willing to cooperate with the study requirements including compliance with the regimen and completion of all office visits;
- Female candidates of child-bearing potential agree to commit to the use of an effective method of contraception (including but not limited to sterilization, barrier devices, oral contraceptives, intrauterine devices (IUDs), condoms, rhythm method, or abstinence) for the duration of the study

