6.10 Subject Withdrawal

Subjects must be informed about their right to withdraw from the clinical investigation at any time and for any reason without sanction, penalty or loss of benefits to which the subject is otherwise entitled. Withdrawal from the clinical investigation will not jeopardize their future medical care or relationship with the investigator. Subjects will be requested to specify the reason for the request to withdraw. The investigator must make all reasonable efforts to retain the subject in the clinical investigation until completion of the clinical investigation.

The investigator may decide to withdraw a subject from the study at any time with reasonable rationale. The subject's future care will not be influenced by a decision, voluntary or otherwise, to withdraw from the study. All reasonable efforts should be made to retain the subject in the clinical study until completion of the study.

Reasons for subject's withdrawal include, but are not limited to:

- Subject refuses to continue participating in the study
- Subject does not meet the inclusion/exclusion criteria and does not require additional follow-up for safety reasons.
- Subject is deceased (cause must be documented)
- Subject's non-compliance
- Subject's participation is terminated by the PI or investigator, although the subject consented, since participation is no longer medically appropriate
- Subject is 'lost to follow up': Subject does not adhere to the scheduled follow up visits but has not explicitly requested to be withdrawn from the clinical study. (This does not apply to missed visits). Site personnel should at all times make all reasonable efforts to locate and communicate with the subject in order to achieve subject compliance to the scheduled follow up visits:
 - A subject will be considered 'Lost to Follow Up' after a minimum of 2 phone calls of a physician or delegate at the investigational site to the subject or contact. These 2 phone calls need to be documented in the subject's hospital records.
 - If these attempts are unsuccessful, a letter should be sent to the subject's last known address or general practitioner (GP) and a copy of this letter should be maintained in the subject's hospital records.

Note: If a subject misses one or more of the scheduled follow up visits (inclusive of the assigned visit windows), this will be considered as a missed visit. The subject may therefore still return for subsequent visits and will not be excluded from the study.

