7.1.1.3 Missing Data

Missing data will be reported at each visit for each outcome. No imputations will be performed for missing data.

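### Undefined non-compliance is a ground for withdrawal and no VAS is planned afterwards, so the 3- and 6-month VAS change may be overstated if that loss is related to pain

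*Combined protocol and SAP*

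**What the plan says.** All references are to the combined protocol and SAP.

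- **Withdrawal grounds (6.10).** The list includes "Subject's non-compliance", with no definition. Separately, "The investigator may decide to withdraw a subject from the study at any time with reasonable rationale".
- **What compliance might mean (5.4.1).** The nearest thing to a definition is in the inclusion criteria. The subject must be willing to follow the regimen and complete the office visits. The subject must also be on stable pain medication and "is willing to stay on those medications with no dose increase until the 3 month visit".
- **After withdrawal (6.10).** The reason goes on a CRF. Follow-up is described only where an adverse event caused the withdrawal, and only for that event. No VAS or other questionnaire is planned.
- **Lost to follow-up (6.10).** The status applies "after a minimum of 2 phone calls of a physician or delegate at the investigational site to the subject or contact". A letter is to follow if the calls fail. No spacing between calls and no earliest date is given. A note on missed visits adds: "The subject may therefore still return for subsequent visits and will not be excluded from the study".
- **Retention (6.10).** The section twice asks for reasonable efforts to keep the subject in the study.
- **Analysis.** Section 7.1.1.1 names repeated measures ANOVA for VAS and does not say how incomplete subjects are handled. Section 7.1.1.3 reports missing data by visit and outcome and states: "No imputations will be performed for missing data". The opening of section 7 says that sensitivity analyses may be in a separate SAP.

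**The concern.** The plan does not separate departing from the regimen from leaving the study. A subject who increases analgesics before month 3, or turns the stimulator off, has arguably failed to comply. Both are plausible responses to returning pain. Section 6.10 then lets the site end participation, and with it VAS collection, even if the subject would still come to the 3- and 6-month visits.

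The study has no control arm, and its primary endpoint is the change in VAS from baseline through the trial period to long-term follow-up. If subjects who do badly leave the later visits more often, the mean among those who remain is too favourable, and nothing specified in the protocol corrects for it. If the repeated measures ANOVA is run on complete cases, which the protocol neither says nor excludes, one missing visit would also remove that subject's earlier values. Section 7.1 says the results may be used to set up a later study with formal hypothesis testing, so an inflated estimate could carry forward.

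**Working it through.** **No figure to reproduce.** Sections 7.1.1.2 and 7.4 give about 60 or up to 60 subjects without a calculation. The protocol states no dropout rate, VAS effect or standard deviation. The loss rates and relief differences below are therefore assumptions.

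**Step 1: can following the plan end VAS collection in a willing subject?**

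1. Section 6.10 allows withdrawal for undefined non-compliance.
2. Section 5.4.1 links compliance to the regimen and the visits, and asks for willingness to hold medication steady until month 3.
3. Section 6.10 plans no VAS after withdrawal.
4. Section 7.1.1.3 imputes nothing.

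So yes, such a loss is permitted. It is not required, and the step from a medication increase or switching off to withdrawal is an inference.

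**Step 2: size of the bias.** Let *d* be the fraction of implanted subjects lost, *Rr* the mean relief in retained subjects and *Rl* the mean relief in lost subjects.

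- True mean = (1 − *d*)·*Rr* + *d*·*Rl*
- Overstatement = *Rr* − true mean = *d*·(*Rr* − *Rl*)

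| Less relief in lost subjects (cm) | *d* = 10% | *d* = 20% |
|---|---|---|
| 0 | 0 | 0 |
| 1 | 0.10 | 0.20 |
| 2 | 0.20 | 0.40 |
| 3 | 0.30 | 0.60 |
| 4 | 0.40 | 0.80 |
| 4.5 | 0.45 | 0.90 |

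The last row is an extreme case. With *Rr* = 4.5 cm and *Rl* = 0, the true mean is 0.90 × 4.5 = 4.05 cm at 10% loss and 0.80 × 4.5 = 3.60 cm at 20%. If lost subjects did better than retained ones, the sign reverses.

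**Step 3: could the analysis repair it?** A simulation of 40,000 subjects (large, so that it shows bias rather than sampling error) assumed 15% loss between months 3 and 6, a true 6-month change of about −3.6 cm, and between- and within-subject SDs of 1.2 cm each. It compared the completer mean with a likelihood-type estimate that uses the earlier visits.

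| Loss depends on | Completer overstatement (cm) | Likelihood-type overstatement (cm) |
|---|---|---|
| Nothing related to pain | 0.00 | 0.00 |
| Observed month-3 VAS | 0.14 | about 0.00 |
| Unseen month-6 VAS | 0.28 | 0.18 |

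A better model removes the bias when loss follows recorded pain. It only reduces the bias when loss follows pain that was never recorded, so collecting the value is the more secure remedy.

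**Step 4: the window.** The footnote to the visit table in section 6.7 puts the last visit at 180 ± 21 days, so it closes on day 180 + 21 = 201.

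**The case against.** The strongest case on the other side is that the protocol already blocks most routes from returning pain to lost data.

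- **Reprogramming.** Sections 1.3, 5.1 and 6 make a change of stimulation parameters the planned response to inadequate relief at any time. A program change is therefore not non-compliance, and loss of relief is not a listed reason for withdrawal. This stands, and it narrows the concern to subjects who raise medication, switch off or otherwise leave the regimen.
- **Missed visits and retention.** The note in 6.10 keeps subjects who miss visits in the study, and the section twice asks for retention efforts. This stands too. It does not limit the non-compliance ground, and it provides no data after withdrawal.
- **Medication.** The no-increase clause is an entry criterion about willingness. Section 9.1 treats failure to follow the plan as a deviation, and no text says that an increase leads to withdrawal. This is why the point is that such a subject could be withdrawn, not that the subject will be.
- **Section 7.** Much of the statistical gap lies there, in the unstated handling of incomplete subjects and the absence of a specified sensitivity analysis. A separate SAP may cover this. Step 3 shows that analysis alone may not be enough.
- **Feasibility.** Sections 7.1 and 7.6 require no formal test and set no success criteria. Missing data and withdrawal reasons are recorded, so attrition would be visible. This limits the consequence to the credibility of the estimate.

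A reader might infer that sites can write subjects off on two calls alone. The text does not support that: two is a minimum, a letter follows, and efforts to locate the subject are required. It does leave the timing open.

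**Conclusion.** The point holds in conditional form. Section 6.10 permits withdrawal for undefined non-compliance, no VAS is planned afterwards and nothing is imputed. A subject who is still willing to attend can therefore lose later VAS values. If that loss is related to pain, the 3- and 6-month change may be overstated by about 0.1 to 0.45 cm at 10% loss and 0.2 to 0.9 cm at 20%. These figures assume 1 to 4.5 cm less relief in lost subjects. They also attribute all of the loss to clauses that could be changed; loss from the subject's own refusal would remain.

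A reader might infer that the primary change is overstated as a matter of fact. The documents do not support that. They give no loss rate and no link between loss and pain, and the bias is zero if lost subjects do not differ. This is a cheap improvement, not a defect that invalidates the study.

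**What to change.** Amend section 6.10 in two places.

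1. Remove non-compliance as a reason to end study participation. Record it as a deviation under section 9.1. State that VAS and the other questionnaires continue at 1, 3 and 6 months where the subject agrees, and that these values enter the primary analysis. Leave unchanged the subject's right to withdraw and the existing ground that participation is no longer appropriate on medical grounds. Do not class protocol-directed program changes as deviations.
2. Assign final lost-to-follow-up status only after the month-6 window has closed (day 201). This agrees with the existing note that subjects who miss visits may return.

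The cost is a few lines of wording, with no new visits, staff or subjects. The small downside is that off-regimen subjects stay in the mean, so the reported change may be less favourable.

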7.1 Hypotheses

This study is an open label, multi-center, feasibility study. Thus, there is no requirement for a formal hypothesis testing. We do anticipate improvements in primary and secondary outcomes. The results obtained in this study will potentially be used to generate a level-1 evidence based study with formal statistical hypotheses testing.

7.1.1 Primary [Safety/Effectiveness] Endpoint Hypothesis(es)

7.1.1.1 Analysis Methodology

The primary analysis to assess improvement in pain intensity, using VAS, will be conducted using repeated measures ANOVA (RMANOVA). Post-hoc Tukey's pairwise comparisons will follow to determine specific differences between follow-up visits. Secondary analyses to assess improvements in quality of life, disability, anxiety, depression catastrophizing and satisfaction will be conducted using repeated measures ANOVA (RMANOVA) or the most appropriate statistical methods.

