1.8 Study Assessments

Subjects will undergo a baseline assessment to collect primary and secondary outcome measures prior to the SCS trial. Specifically, baseline assessments will include: pain rating as assessed by the VAS, quality of life as assessed by EQ-5D, disability as assessed by ODI, anxiety and depression as assessed by the HADS, and pain catastrophizing as assessed by the PCS. Medication usage will also be collected during the baseline visit.

Subjects will be implanted with trial SCS system according to clinical practice and practitioner's discretion. At the end of the SCS trial period, subjects who experienced a reduction of 50% or more in average pain back and/or leg VAS scores with one of the two microdosing stimulation paradigms will be offered permanent implant and further participation in the study. The same primary and secondary outcomes measures will be collected at the end of the SCS trial period as well as at the 1, 3 and 6 months follow up visit, with the inclusion of patient satisfaction as assessed by the PGIC. Programming parameters will also be assessed during these visits.

2 Introduction

This document is a clinical investigation plan (CIP) for the BOLD clinical investigation. This clinical investigation is intended to evaluate the therapeutic efficacy of microdosing BurstDR[™] stimulation in

spinal cord stimulation (SCS) patients with chronic intractable back and/or leg pain. This clinical investigation is sponsored by Abbott.

This clinical investigation will be conducted in accordance with this CIP. All parties involved in the conduct of the clinical investigation will be qualified by education, training, or experience to perform their tasks and this training will be documented appropriately.

3 Background and Justification for Clinical Investigation

Spinal cord stimulation (SCS) is increasingly being used as an alternative for the treatment of chronic, intractable pain. In a systematic meta-analysis of the literature, Taylor et al. (2006) reported that SCS reduces pain, improves quality of life, reduces analgesic use, allows some patients to return to work and may also result in significant cost savings over time, while having minimally significant adverse events in patients with neuropathic back and/or leg pain.

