5.3.1 Primary Endpoint

• Evaluate the change in pain intensity between baseline, trial and long-term follow up evaluations using the Visual Analog Scale (VAS) assessments.

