6.4.2 SCS Trial

During the trial implant phase, SCS leads will be implanted in the dorsal column based on physician discretion. According to standard clinical practices performed in the United States (US), the trial phase will last around 3-7 days. At the start of the trial phase, patients will be programmed with the first ON/OFF stimulation pattern (30 second STIM ON, 90 seconds STIM OFF). Patients who do not achieve adequate pain relief (at least 50% reduction in back and/or leg VAS from baseline) within the first 3-4 days will be reprogrammed to a new ON/OFF stimulation pattern (5 seconds ON/ 15 seconds OFF). Patients, who still do not achieve adequate pain relief within 2 to 3 days from reprogramming, will be reprogrammed to a continuous mode of BurstDR[™] stimulation and their trial evaluation will continue. These patients will be evaluated for an additional 2 days. At the end of the SCS trial, all subjects that experience at least 50% pain relief (according to average back and/or leg VAS) using one of the two microdosing burst stimulation paradigms will be considered further participation in the study. Patients who still do not achieve adequate

pain relief will be reprogrammed to a continuous mode of BurstDRTM stimulation and their trial evaluation will continue. These patients will be evaluated for an additional 2 days.

The following assessments and information will be collected at the SCS Trial visit

- Surgery Form
- Clinical investigation specific examinations
 - Programming Form

The following activities will be performed at the SCS Trial visit:

- SCS Trial Lead(s) Implant
- EPG Device programming

Timing of visit	Activities at visit	Case Report Form	
SCS Trial	SCS trial lead implant	Surgery Form	
	EPG programming	Programming Form	

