6.4.3 End of Trial

During the End of Trial visit, subjects will complete the same questionnaires completed during the baseline visit. If the VAS score is < 50% of the VAS collected during the screening visit and is not using the two microdosing burst stimulation paradigms, the subject will exit the study. Subjects whose VAS score at the end of the trial is >50% of the VAS collected during the screening visit and is using one of the two microdosing burst stimulation paradigms, will be considered for permanent lead and IPG implantation.

The following assessments and information will be collected at the End of Trial visit:

- Clinical investigation specific examinations
 - Pain level as assessed by the VAS
 - Quality of life as assessed by the EQ-5D
 - Disability as assessed by the ODI
 - Anxiety and Depression as assessed by the HADS
 - Pain Catastrophizing as assessed by the PCS
 - Satisfaction as assessed by the PGIC
 - Medication usage;
 - Programming Form

Timing of visit	Activities at visit	Case Report Form
End of Trial	 Subject assess pain levels, quality of life, disability, anxiety, depression, pain catastrophizing, satisfaction, medication usage, and programming 	 VAS Form EQ-5D Form ODI Form HADS Form PCS Form PGIC Form Medication Usage Form Programming Form

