If a subject withdraws from the clinical study, the site will record the subject's reasons for withdrawal, on a Withdrawal CRF.

When subject withdrawal from the clinical study is due to an adverse event the subject will be followed until resolution of that adverse event or determination that the subject's condition is stable. The status of the subject's condition should be documented at the time of withdrawal.

The third follow up visit will be the final study visit. The subject will complete the questionnaires as in the previous follow up visit and will exit the study.

7 Statistical Considerations

The following section describes the statistical methods for the clinical investigation and justification of the design. Additional details on statistical analyses, including sensitivity analyses, poolability analyses, subgroup analyses and analysis of descriptive endpoint(s) may be maintained in a separate Statistical Analysis Plan (SAP).

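### The primary VAS analysis names no analysis set and no rule for incomplete subjects, and its follow-up changes are conditional on microdosing trial success

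*Combined protocol and SAP*

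**What the plan says.** - **Endpoint (5.3.1):** "Evaluate the change in pain intensity between baseline, trial and long-term follow up evaluations using the Visual Analog Scale (VAS) assessments". Follow-up visits are at 1, 3 and 6 months after activation (6.4.6).
- **Analysis (7.1.1.1):** "The primary analysis to assess improvement in pain intensity, using VAS, will be conducted using repeated measures ANOVA (RMANOVA"), followed by Tukey pairwise comparisons. Section 7.3 sets tests at 0.05.
- **Missing data (7.1.1.3):** missingness is to be reported for each visit and outcome, and "No imputations will be performed for missing data". Section 6.10 lets a subject who misses a visit stay in the study and return later.
- **Further detail (opening of section 7):** it "may be maintained in a separate Statistical Analysis Plan (SAP"). The contents listed there do not include analysis sets.
- **Gate to follow-up:** section 1.8 says that subjects with a VAS reduction of 50% or more "with one of the two microdosing stimulation paradigms will be offered permanent implant and further participation in the study". Section 6.4.2 says that those with at least 50% relief "using one of the two microdosing burst stimulation paradigms will be considered further participation in the study". Sections 1.3, 5.1 and 6 agree.
- **Trial failures (6.4.2):** those who "still do not achieve adequate pain relief within 2 to 3 days from reprogramming, will be reprogrammed to a continuous mode" of stimulation and are observed for two more days.
- **End of Trial visit (6.4.3):** if VAS is below 50% of the screening value and the subject is not on microdosing, "the subject will exit the study". Subjects on microdosing with VAS above 50% of the screening value are considered for implant.

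**The concern.** The primary analysis can be run on at least two different populations, and the text does not choose between them. If complete rows are required, even the baseline to end-of-trial contrast is limited to subjects who passed the trial and attended every visit. If all available values are used, the early visits hold everyone trialled and the later visits hold passers only. Neither version gives a result per patient who starts the SCS trial.

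This matters because the primary objective (5.2.1) concerns patients who have never had neuromodulation, long-term efficacy is a secondary objective (5.2.2), and the results may feed a later level-1 study (7.1). The end-of-trial VAS is also both the gate and an analysed visit, so contrasts that start from it contain regression to the mean.

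**Working it through.** The plan derives no figure that could be reproduced: the 60 subjects have no stated effect size, SD, pass rate or dropout (7.1.1.2). Everything below is illustration. From the documents come only N = 60, the 6.0 cm entry floor, the 50% gate (1.8 and 6.4.2 wording) and three follow-up visits.

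**1. Gate floor.** Where entry and gate use the same VAS, a passer has fallen by at least 0.5 × 6.0 = 3.0 cm. A large end-of-trial change is built in for everyone with follow-up data.

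**2. Complete cases.** Let s be the pass rate and m the chance of missing each follow-up visit, independently. Complete rows = 60 × s × (1 − m)³. Implanted subjects dropped = 60 × s × [1 − (1 − m)³].

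| s | m | Complete rows | Implanted but dropped |
|---|---|---|---|
| 0.50 | 0.05 | 25.7 | 4.3 |
| 0.50 | 0.10 | 21.9 | 8.1 |
| 0.80 | 0.05 | 41.2 | 6.8 |
| 0.80 | 0.10 | 35.0 | 13.0 |

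That gives 22 to 41 complete rows, with 4 to 13 implanted subjects (14% to 27%) dropped.

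**3. Denominator and reference visit, by simulation.** Assumptions: true baseline N(7.2, 1.3) cm with observed baseline at least 6; true proportional relief N(45%, 30%) or N(60%, 20%), truncated to −20% to 100% and constant after the trial; visit noise SD 0.8 or 1.2 cm. A subject passes if VAS is at or below half of baseline at a first look or, failing that, a second. Responders over all trialled = pass rate × responder rate in passers.

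| Mean relief / noise SD | Pass | 6-month responders, passers | Responders, all trialled | End of trial to month 6 |
|---|---|---|---|---|
| 45% / 0.8 | 0.520 | 0.769 | 0.400 | +0.32 cm |
| 45% / 1.2 | 0.570 | 0.707 | 0.403 | +0.61 cm |
| 60% / 0.8 | 0.773 | 0.822 | 0.635 | +0.25 cm |
| 60% / 1.2 | 0.798 | 0.773 | 0.617 | +0.47 cm |

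In whole subjects, this is 24/31 (77%) against 24/60 (40%, exact 95% CI 28-53%), or 38/46 (83%) against 38/60 (63%, CI 50-75%).

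The last column arises with no true change: passers are selected partly on favourable noise. VAS then rises, against the device. The same interval also spans a change of program. Both trial patterns, 30 s on / 90 s off and 5 s on / 15 s off, are 1:3, while the post-implant search starts at 1:12 (sections 6 and 6.4.2).

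**4. Denominator effect in cm, the endpoint's own unit.** A separate simulation assumed baseline N(7.5, 1.2) truncated to 6-10 cm, mean relief 30-60%, between-subject SD 15-30 points and noise SD 1.0-1.5 cm. The 6-month reduction in passers exceeded the value for everyone, had all been followed with the same true relief, by 0.45 to 2.15 cm. With mean relief 50%, SD 25 points and noise 1.0 cm, half pass, and the reductions are 5.1 cm (passers) and 3.8 cm (everyone).

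**5. Missingness among implanted subjects.** Assume that 5% miss a visit after at least 50% relief at the prior visit, and otherwise 20% or 35% do. Complete-case analysis then overstates the 6-month reduction by 0.07 to 0.24 cm. A mixed model leaves 0.03 to 0.11 cm, a gain of about 0.04 to 0.13 cm.

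**6. Missing 6-month VAS counted as non-response.** If 5-10% of implanted subjects lack it, the all-trialled responder figure falls by 0.05 × 40.0 = 2.0 to 0.10 × 63.5 = 6.4 percentage points.

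**The case against.** The study is a feasibility study with no formal hypothesis and no success criteria (7.1, 7.6). The gate is stated openly and repeatedly. Missing data are to be reported by visit, and the End of Trial forms would let anyone derive the pass rate. The responder contrast concerns an outcome that the plan does not define. The bias from dropping incomplete rows is small even under fairly heavy missingness in poor responders. All of this stands and limits the severity. It does not say which subjects enter the primary model.

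Some stronger readings are tempting but unsupported:

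- **That the gate conceals a bias, or that the plan claims durability.** It does neither. The gap is in denominator and labelling, and the end-of-trial drift runs against the device.
- **That month 1 is contaminated because a weekly rating used to choose the program doubles as the month-1 VAS.** The text places weekly evaluation in the month before that visit (5.1) and a VAS Form at the visit itself (6.4.6, 6.7). Figure 2 is not available to show otherwise.
- **That month 3 is a clean reference.** Reprogramming is allowed at any time (section 6), and the commitment to no dose increase ends at the 3 month visit (5.4.1). Month 3 to 6 is therefore open to medication change.

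**Conclusion.** The point holds. As written, the primary RMANOVA has no analysis set and no rule for incomplete subjects. The 1, 3 and 6 month changes describe microdosing trial successes only; a subject relieved only on continuous stimulation does not proceed under 1.8 and 6.4.2. End of trial to follow-up mixes regression to the mean with a program change and cannot be read as loss or maintenance of effect.

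The denominator is the main effect: 71-82% responders among passers against 40-64% of all trialled. Listwise bias is minor. These sizes depend on assumed relief, noise, pass and missingness rates, none of which the documents give. That follow-up is conditional on the end-of-trial gate does not depend on those values.

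Section 6.4.3 conflicts with 1.8 and 6.4.2: VAS above 50% of the screening value means less than 50% reduction. The arithmetic uses the 1.8 and 6.4.2 wording without judging which is intended. Overall severity is modest; the change should be made, but the study does not fail without it.

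**What to change.** 1. In 7.1.1.1, define a trialled set (all who started the SCS trial) and an implanted set. Replace RMANOVA with a likelihood-based mixed model for repeated measures on all available VAS in implanted subjects. Label the 1, 3 and 6 month changes as conditional on microdosing trial success.
2. Over the trialled set, report the microdosing pass rate and, as an added descriptive summary, the proportion with at least 50% VAS reduction at 6 months, both with exact CIs. Count trial failures and exits as non-responders. State in 7.1.1.3 how an implanted subject with no 6-month VAS is counted.
3. Report baseline to end-of-trial VAS change for all trialled subjects by the stimulation mode on the Programming Form. Do not attribute values on continuous stimulation to microdosing.
4. State that end of trial to follow-up is not evidence of lost or maintained effect. Where follow-up visits are compared with each other, note the possible reprogramming and the end of the medication commitment at month 3.
5. Reconcile the gate wording in 6.4.3 with 1.8 and 6.4.2.

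The cost is wording in section 7, reconciliation of the gate text, a little more analysis, and an added summary less favourable than one among passers. No new data or patients are needed.
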